Plasma CBD, Delta-9 THC, 11-Hydroxy Delta-9 THC, Delta-9 Carboxy THC, and Anandamide levels will be assessed prior to the first dose (T1), 45 min after ingesting the first dose (T1), and 45 min after ingesting the morning dose after 1 day (T2, T5), 1 week (T3, T6), and 4 weeks (T4, T7) of treatment with each dose of CBD (600mg/day, 1200mg/day). Anandamide levels will also be assessed at these timepoints in placebo treated participants. We will also assess pre-CBD dosing plasma levels of CBD and Anandamide prior to ingesting the morning dose after 1 week (T3, T6) and 4 weeks (T4, T7) of treatment with each dose of CBD. Anandamide levels will also be assessed at these timepoints in placebo-treated participants.

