5.1.1 Primary Study Endpoints

Circulating cannabinoid levels

Circulating levels of CBD, Anandamide, Delta-9 THC, 11-Hydroxy Delta-9 THC and Delta-9 Carboxy THC will be assessed in CBD-treated participants 45 minutes after the initial administration (T1, T4), 1 day (T2, T5), 1 week (T3, T6), and 4 weeks (T4, T7) of treatment with each dose of CBD. Anandamide levels will also be assessed at these timepoints in placebo treated participants. Additionally, circulating levels of CBD and anandamide will be assessed in CBD-treated participants 12 hours after ingestion of the preceding evening dose following 1 week (T3, T6) and 4 weeks (T4, T7) of administration of each dose of CBD. Plasma CBD levels will be determined via High Performance Liquid Chromatography/Tandem Mass Spectrometry (LC-MS/MS) by collaborators at the Nathan Kline Institute.

Safety

Safety will be assessed by collection of adverse events at all visits after treatment is initiated. LFTs will be obtained at screening, as well as weeks 4, 8, and 9 to assess liver function during and after treatment with study medication. Risk of suicidality will be assessed using the Columbia-Suicide Severity Rating Scale (C-SSRS) [111] by a licensed Clinical Psychologist, NP or MD as part of each study visit (except for the 1-day/T2 and 4 weeks+1-day/T5 visits).

Psychomotor and subjective effects of CBD:

Basic motoric and cognitive function will be evaluated throughout treatment with several established field sobriety tests, including a walk-and-turn task, one-leg stand, Romberg's test, finger-finger test, and counting backwards [97]. The Addiction Research Center Inventory (ARCI), 49-item version [98], will be used as a measure of the intoxicating effects and abuse potential of CBD. Breath Alcohol Concentration (BAC) will also be measured to ensure participants are not under the influence of alcohol during administration of these tasks. Between-group differences on psychomotor tasks (T1-T8), cognitive measures (T3, T6) and number of adverse events (T1-T9) will be assessed.

Cognitive Function:

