7.1.5 Dosing and Administration

Participants will self-administer CBD vs Placebo twice daily for a total of 600mg/day CBD vs. Placebo for the first four weeks of treatment and 1200mg/day CBD vs. Placebo for weeks 5-8 of treatment. For the first four weeks of treatment, participants will self-administer two 200mg capsules every morning following a light meal at approximately the same time of day, and an additional single 200mg capsule approximately 12 hours later following a light meal. During weeks 5-8 of treatment, participants will self-administer three 200mg capsules every morning following a light meal at approximately the same time of day, and an additional three 200mg capsules approximately 12 hours later following a light meal.

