21.3.2 Analysis of the Primary Endpoint(s)

For Hypothesis 1a, acute circulating levels of CBD will be assessed in CBD-treated participants 45 minutes after initial administration (T1, T4), and 45 minutes after administration of the morning dose of medication following 1 day (T2, T5), 1 week (T3, T6), and 4 weeks (T4, T7) of treatment with each dose of CBD. Additionally, circulating levels of CBD will be assessed in CBD-treated participants 12 hours after ingestion of the preceding evening dose following 1 week (T3, T6) and 4 weeks (T4, T7) of administration of each dose of CBD. Levels of CBD (mean and standard deviation) will be reported at each timepoint and effects of dose and timepoint will be evaluated. For Hypothesis 1b, circulating CBD levels (mean and standard deviation) 45 minutes after administration of the morning dose of medication following 1 week (T3, T6) and 4 weeks (T4, T7) of treatment with each dose of CBD will be reported in CBD-treated participants. For Hypothesis 1c, between-group differences on psychomotor tasks (T1-T8), cognitive measures (T3, T6) and number of adverse events (T1-T9) will be assessed.

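### The dose effect on CBD levels is labelled 600 vs 1200 mg/day, but the 12-hour and 45-minute samples follow different dose ratios (3.0 and 1.5), and the T4 45-minute sample carries two labels

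*Combined protocol and SAP*

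**What the plan says.** Section 21.3.2 (Analysis of the Primary Endpoint(s)) states: "Levels of CBD (mean and standard deviation) will be reported at each timepoint and effects of dose and timepoint will be evaluated". Section 3.2.3 shows what dose means here, describing sampling at set times "of treatment with each dose of CBD (600mg/day, 1200mg/day").

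Section 7.1.5 gives the daily totals, "for a total of 600mg/day CBD vs. Placebo for the first four weeks of treatment and 1200mg/day CBD vs. Placebo for weeks 5-8", and how each is divided. In weeks 1-4 participants "will self-administer two 200mg capsules every morning following a light meal at approximately the same time of day, and an additional single 200mg capsule" about 12 hours later. In weeks 5-8 they take "three 200mg capsules every morning following a light meal at approximately the same time of day, and an additional three 200mg capsules" about 12 hours later.

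Sections 5.1.1 and 21.3.2 tie the two kinds of sample to different intakes. The pre-dose sample is taken "12 hours after ingestion of the preceding evening dose following 1 week (T3, T6) and 4 weeks (T4, T7"). The acute sample is taken 45 minutes after the morning dose.

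For T4, section 7.3.1 puts the first intake of each dose level on site, at T1 and T4. Section 8.3.3.3 schedules one pre-dose and one 45-minute sample at that visit. Sections 5.1.1, 21.3.2 and 21.3.4 list T4 both as the initial administration of the second level and as 4 weeks on the first.

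Section 21.3.1 specifies a mixed model with treatment group, time and subject. It names no dose term and no term separating pre-dose from 45-minute samples.

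**The concern.** Circulating levels are part of the primary objective, and dose and timepoint are the only effects named for them. A reader shown a dose effect labelled 600 vs 1200 mg/day will compare it with a doubling. Because the morning/evening split changes between periods, neither sampling time carries a 2-fold contrast in the amount last taken. A departure from 2 at either time could come from the split alone and be read as a property of the drug.

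T4 adds a labelling error. If its 45-minute level follows a 600 mg morning intake but is filed under 600 mg/day, the week-1 to week-4 comparison at 45 minutes (T4 vs T3) contains a dose change. The between-level comparison at week 4 (T7 vs T4) then has none in the amount last taken. Both named effects are touched.

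**Working it through.** **Reproducing the plan's figures.** From the capsule counts in 7.1.5: weeks 1-4, 2 × 200 + 1 × 200 = 600 mg/day; weeks 5-8, 3 × 200 + 3 × 200 = 1200 mg/day. The labelled ratio is 1200/600 = 2.0.

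**Amount last taken before each sample** (7.1.5 with 21.3.2; T4 by 7.1.5, 7.3.1 and 8.3.3.3):

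| Comparison | First level | Second level | Ratio |
|---|---|---|---|
| 12-hour, T6 vs T3 and T7 vs T4 | 200 mg evening | 600 mg evening | 3.0 |
| 45-minute, T6 vs T3 | 400 mg morning | 600 mg morning | 1.5 |
| 45-minute, T7 vs T4 | 600 mg morning | 600 mg morning | 1.0 |

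**12-hour level under dose-proportional kinetics.** The documents give no half-life, so 3 to 60 h is assumed. Let r = 2^(−12/half-life) be the fraction remaining after 12 hours. At steady state, with absorption complete by 12 hours, the ratio is

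(600 + 600r)/(200 + 400r) = 3(1 + r)/(1 + 2r).

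This exceeds 2 whenever 3 + 3r > 2 + 4r, that is, for every r below 1.

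| Half-life | r | Ratio |
|---|---|---|
| 3 h | 0.0625 | 2.83 |
| 6 h | 0.25 | 2.50 |
| 12 h | 0.50 | 2.25 |
| 24 h | 0.707 | 2.12 |
| 60 h | 0.871 | 2.05 |

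**45-minute level under the same kinetics.** Let a and b be the summed contributions per mg of all morning and all evening doses at the sampling moment. At steady state the ratio is (600a + 600b)/(400a + 200b) = 3(a + b)/(2a + b), which is below 2 only if a > b. That depends on how much of the morning dose has been absorbed by 45 minutes. A one-compartment oral model was summed over all doses given, with absorption rates of 0.3 to 2 per hour and lags of 0 to 0.5 h (both assumed). Each mg contributes ka/(ka − k) × [exp(−k(t − lag)) − exp(−ka(t − lag))], where k = ln 2/half-life. T6/T3 at 45 minutes:

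| Half-life | Absorption rate | Lag | Ratio |
|---|---|---|---|
| 3 h | 2/h | 0 | 1.56 |
| 6 h | 2/h | 0 | 1.71 |
| 6 h | 0.5/h | 0 | 1.94 |
| 6 h | 0.5/h | 0.5 h | 2.18 |
| 6 h | 0.3/h | 0.5 h | 2.28 |
| 12 h | 1/h | 0 | 1.93 |
| 24 h | 1/h | 0 | 1.98 |

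At 60 h, accumulation is incomplete after one week and the ratio is 2.10 to 2.20. The range overall is about 1.6 to 2.3.

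**T4 at 45 minutes.** With a half-life of 6 h, absorption of 2/h and no lag, the T7/T4 ratio is 1.22 if 600 mg was taken at T4 and 1.71 if 400 mg was taken. Levels at T6 and T7 are equal in this case, so T4/T3 would be 1.71/1.22 = 1.40: an apparent 40% rise from week 1 to week 4 on a supposedly constant dose. With slow, lagged absorption (0.3/h, 0.5 h) it is 2.28/2.08 = 1.10.

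**What the split leaves alone.** Hypothesis 1a and the accumulation summary in 21.3.4 compare 12-hour levels at T3 with T4 and at T6 with T7. The preceding evening dose is 200 mg at both visits of the first pair and 600 mg at both of the second, and the T4 pre-dose sample comes before any change. The split cancels.

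**The case against.** The best defence is that the plan states no dose-proportionality aim. Comparing levels under the two regimens as given is legitimate, the split is disclosed in 7.1.5, levels are reported by timepoint, and a formal SAP is still to come (21.1). At a single sampling time with one visit per level, renaming a two-level dose factor changes neither its test nor the estimated difference. All of this stands. It means the regimen comparison is not invalid in itself; the problem is a label that invites reading it as the effect of doubling the dose.

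The defence does not reach T4, where a sample sits in the wrong cell and recoding changes the estimates. Nor does it say how the two kinds of sample enter a model that has no term to separate them.

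Two stronger readings are tempting and should be resisted. A reader might infer from 3.0 and 1.5 that the dose effect is biased upward at 12 hours and downward at 45 minutes. The upward bias at 12 hours follows under linear kinetics. The downward one needs fast absorption, and the documents give neither an absorption rate nor a half-life. A reader might also infer that the accumulation check is compromised. It is made within each dosing period, so the split does not affect it.

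**Conclusion.** The point holds in a limited form. The milligram ratios (3.0 and 1.5 against a labelled 2.0) follow directly from the documents. The 12-hour excess over 2 rests on linear kinetics at steady state; its size, about 2.05 to 2.83, depends on the assumed half-life. At 45 minutes the expected ratio is about 1.6 to 2.3, and its direction cannot be settled from the documents.

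The T4 conflict is one of labelling: read together, 7.1.5, 7.3.1 and 8.3.3.3 place the 45-minute sample after a 600 mg intake, while 21.3.2 also counts it as 4 weeks on 600 mg/day. As written, T4 vs T3 and T7 vs T4 at 45 minutes are mislabelled.

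Hypothesis 1a's pre-dose comparison is unaffected. Hypothesis 1b's summary at 1200 mg/day uses T6 and T7, where the amounts are not in doubt. This should be corrected in the formal SAP; it does not invalidate the endpoint.

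**What to change.** In 21.3.2 and the formal SAP:

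- Analyse the 12-hour and 45-minute samples separately.
- Code each sample by the doses that precede it, and report the amount last taken beside each mean and standard deviation.
- Where a pre-dose level is drawn at the same visit, also analyse the 45-minute rise above it against the morning dose given at that visit.
- Describe the 600 vs 1200 mg/day contrast as one between regimens. Judge any statement on proportionality against the ratio expected from the actual split, over a stated range of half-life and absorption.
- Reconcile the label of the T4 45-minute sample across 5.1.1, 7.1.5, 7.3.1, 8.3.3.3, 21.3.2 and 21.3.4, so that it enters the analysis once, under the intake it actually followed.

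The cost is SAP wording and slightly more analysis, with no dosing change and no new data. The rise above pre-dose is not available at T2 and T5, where no pre-dose sample is drawn. It is also only approximately proportional to the morning dose, because the contribution of earlier doses keeps changing during the 45 minutes.

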3.2.1 Preclinical Data

In rodent models, CBD reduces cue-induced heroin seeking, potentiates extinction of cocaine- and amphetamine-induced conditioned place preference [73], and normalizes heroin-seeking-induced changes in glutamatergic GluR1-containing amino-hydroxy-methyl-isoxazolepropionic (AMPA) receptors and CB1 receptor expression in the nucleus accumbens [74]. Work done in the laboratory of [name] (consultant on the current proposal) demonstrated that transdermal CBD at a dose yielding serum CBD concentrations of 300-400ng/ml reduces stress- and cue-induced alcohol- and cocaine- seeking in rodents, with effects lasting up to 138 days post-CBD treatment for alcohol [75]. This regimen also reduced anxiety-like behavior in alcohol-exposed, cocaine-exposed, and drug-naïve rodents without impacting locomotor activity or cue- or stress- induced reinstatement for a sweet solution, and reversed impulsive-like behavior induced by alcohol intoxication in a delay discounting task 6-15 days after the cessation of treatment. Another recent report also demonstrated CBD's ability to reduce the reinforcing effects of alcohol at an identical dose of CBD delivered subcutaneously in a microparticle formulation also designed to provide continuous controlled release of CBD [76].

Studies of CBD's effects on addiction-related behaviors in human participants are limited. The only study to assess the impact of CBD on alcohol-related behaviors found no impact of 200mg of CBD on symptoms of intoxication in healthy volunteers [77]. However, high concentrations of CBD in cannabis are related to lower attentional bias toward drug stimuli and lower self-rated liking of cannabis-related stimuli relative to cannabis with a low ratio of CBD to THC [78], CBD may reduce cigarette smoking in dependent humans [79], and a single case study reported that daily CBD prevented marijuana withdrawal symptoms [80].

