3.2.3 Dose Rationale (if applicable)

CBD has been given up to 600 mg daily orally for cannabis dependence [80], and the one existing human study of CBD's impact on the acute effects of alcohol used a dose of 200 mg [88]. CBD was given to patients with schizophrenia up to 1280 mg/day [89], and Phase 3 trials of CBD for seizure disorders used doses of 20 mg/kg/day oral CBD solution (1400 mg/day for a 70 kg person) [9, 11].

Consistent and clinically significant effects on fear and anxiety in the absence of intoxicating, psychotomimetic, and psychotropic effects have been observed with oral dosing in the range of 300-600 mg/day [90]. However, preliminary work performed by [name] and others [76] indicates that higher doses (>30mg/kg/day transdermal/subcutaneous) yielding serum CBD concentrations in the range of 300-400ng/ml are required to reduce alcohol-reinforced reward-seeking behaviors in rodents.

Oral dosing of CBD is complicated by limited oral absorption, which is similar to THC at approximately 6% [91], and by the possibility that high doses of CBD could convert to THC when delivered orally [92, 93]. However, oral delivery of CBD in a sesame-oil formulation at a dose of 12mg/kg (roughly equivalent to 1000mg/day adjusted for average human body weight) was shown to yield serum concentrations within the targeted range in rats [94]. We therefore will administer CBD vs. Placebo orally in a lipid-based formulation at 600mg/day for an initial period of 4 weeks, followed by 1200mg/day for an additional 4 weeks, to reach our target circulating levels of 300-400ng/ml in a human AUD sample. Two studies in humans have shown no progressive accumulation of CBD levels with repeated daily dosing, including following 6 weeks of oral administration of 700mg/day CBD [95, 96], and preliminary data with transdermal CBD up to 30mg/kg/day in rodents shows no serum accumulation over 7 days of treatment ([name], unpublished data). Therefore, under the proposed dosing regimen we expect to achieve steady-state circulating levels of CBD within a week.

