21.2 Statistical Hypotheses

Hypothesis 1a: Within-group circulating CBD levels will stabilize within one week, i.e. pre-CBD dosing (12 hour) levels obtained after 1 week of treatment will not differ from those obtained after 4 weeks of treatment at each dose.

Hypothesis 1b: Circulating CBD levels obtained at the 1200 mg/day dose will be comparable to those associated with anti-additive effects in animal models, i.e., in the range of 200-400 ng/ml.

Hypothesis 1c: No clinically significant cognitive or motoric impairments, CBD-related serious adverse events, or persisting adverse effects will be observed.

Hypothesis 2a: Relative to placebo, CBD will improve self-report measures of craving, anxiety, mood, and self-efficacy.

Hypothesis 2b: Relative to placebo, CBD will be associated with decreased stress- and alcohol cue-induced craving and physiological stress response

Hypothesis E: Relative to the placebo-treated group, CBD-treated participants will have fewer heavy drinking days during and for four weeks after treatment with 1200mg/day CBD vs. placebo.

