21.3.4 Safety Analyses

Means and standard deviations of acute circulating CBD and THC levels within CBD-treated participants 45 minutes after initial administration (T1, T4), and 45 minutes after administration of the morning dose of medication following 1 day (T2, T5), 1 week (T3, T6), and 4 weeks (T4, T7) of treatment with each dose of CBD will be assessed to determine whether target circulating levels of CBD have been achieved, and whether metabolic transformation of CBD to THC has occurred.

Means and standard deviations of change in 12 hour circulating CBD levels from 1 week to 4 weeks of treatment (T3 to T4, and T6 to T7) within CBD-treated participants will be presented to determine whether extended treatment with CBD results in accumulation of CBD.

The number of participants within each treatment group that were able to pass a battery of psychomotor field sobriety tasks (walk-and-turn task, one-leg stand, Romberg's test, finger-finger test, and counting backwards [97]) within 2 hours of the initial administration of each dose of CBD vs. placebo (T1 and T4) will be analyzed as summary statistics during treatment.

AEs and SAEs, when present, will be collected on an AE Case Report Form at study visits. The form will include an assessment of clinical significance and study relatedness. Serious Adverse Events (SAEs) will be documented on an additional SAE form. These CRFs will be based on those used in recent NIDA Clinical Trials Network trials. To further assess abuse potential, visual analog scales will be used to assess abuse potential. Scales will include desire to use the study medication again, desire to use the study medication again for pleasurable intoxication ("to get high"), and craving for the study medication.

The study may be stopped if there are untoward and concerning levels of Adverse Event (AE) or Serious Adverse Event (SAE) outcomes attributable to CBD or study participation. If the DSMB finds it is likely that CBD is contributing to negative outcomes, they will consider solutions including protocol changes or potentially stopping the study.

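### Hypothesis 1b and the target-level check compare only the 45-minute post-dose CBD level with the target; the 12-hour pre-dose levels from the same visits should be compared with it too

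*Combined protocol and SAP*

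**What the plan says.** **Hypothesis.** Section 21.2 states: "Circulating CBD levels obtained at the 1200 mg/day dose will be comparable to those associated with" anti-addictive effects in animals, given as "in the range of 200-400 ng/ml". Section 4.1 makes the same prediction within the primary objective. Neither section names a sampling time for 1b.

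**Analysis.** The sampling time appears only in Section 21.3.2: "For Hypothesis 1b, circulating CBD levels (mean and standard deviation) 45 minutes after administration of the morning dose of medication", after 1 week and 4 weeks at each dose. Section 21.3.4 lists only 45-minute draws and says that they "will be assessed to determine whether target circulating levels of CBD have been achieved".

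**Pre-dose levels.** Levels 12 hours after the evening dose are drawn at T3, T4, T6 and T7. Section 21.3.2 lists them under Hypothesis 1a (stability) and Section 21.3.4 uses them for accumulation. Section 21.3.2 also promises the mean and SD of CBD at every timepoint, so they will be reported. No section sets them against the target.

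**Benchmark.** Section 3.2.1 describes one rodent study in which "transdermal CBD at a dose yielding serum CBD concentrations of 300-400ng/ml reduces stress- and cue-induced alcohol- and cocaine- seeking in rodents", and a second at the same dose "delivered subcutaneously in a microparticle formulation also designed to provide continuous controlled release of CBD". Section 3.2.3 gives the aim of human dosing as "to reach our target circulating levels of 300-400ng/ml in a human AUD sample".

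**Human dosing.** Under Section 7.1.5, oral capsules are taken twice daily about 12 hours apart, in equal halves at 1200 mg/day. The schedule of assessments labels the post-dose draw as the peak.

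**The concern.** The benchmark is a level produced by delivery designed to release drug continuously. The second rodent study is described as also having that design, which implies that the transdermal regimen had it too. The human level comes from intermittent oral dosing and rises and falls within each 12-hour interval. One sample, 45 minutes into the interval, does not show where the level lies for the rest of it.

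The hypothesis speaks of circulating levels in general, and the narrowing to 45 minutes in the analysis text is not explained. If the 45-minute mean is in range, the plan's wording permits a statement that exposure was comparable to the animal work, even if the pre-dose level at the same visit is well below the range. A reader trying to interpret a null result on craving or drinking would naturally look to 1b to judge whether adequate exposure was reached.

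**Working it through.** The plan gives no threshold, test, margin or power for 1b (Section 21.4 omits it), so there is no figure to reproduce. The check asks how far a 45-minute level can differ from the rest of the interval.

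**Inputs from the documents**
- Range: 200-400 ng/ml (Sections 4.1, 21.2) or 300-400 ng/ml (Section 3.2.3).
- Dosing interval: about 12 h, equal doses at 1200 mg/day (Section 7.1.5).
- Sampling: 45 min (0.75 h) after the dose, and 12 h after the preceding dose.

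**Assumptions (not in the documents)**
- A 45-minute level of 300 ng/ml, inside the 200-400 range.
- Half-life (t½) of 4, 8, 12 or 24 h.
- Absorption rate constant (ka) of 3 per h (fast) or 0.5 per h (slow).

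**Step 1: log-linear decline from 45 minutes.** The time left to the 12-hour sample is 12 − 0.75 = 11.25 h, so C12 = C0.75 × 2^(−11.25/t½).
- t½ 4 h: 300 × 0.142 = 43 ng/ml
- t½ 8 h: 300 × 0.377 = 113 ng/ml
- t½ 12 h: 300 × 0.522 = 157 ng/ml
- t½ 24 h: 300 × 0.723 = 217 ng/ml

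The half-life needed to stay at or above a floor F is 11.25 × ln 2 / ln(C0.75/F).
- From 300 with floor 200: 19.2 h
- From 400 with floor 200: 11.25 h
- From 400 with floor 300: 27.1 h

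**Step 2: steady-state oral model.** One compartment with first-order absorption, dosed every τ = 12 h, with k = ln 2 / t½. C(t) is proportional to e^(−kt)/(1 − e^(−kτ)) − e^(−ka·t)/(1 − e^(−ka·τ)), scaled so that C(0.75 h) = 300 ng/ml. Levels are in ng/ml.

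| ka (per h) | t½ (h) | 12-h level | Peak | Interval average | Time below 200 |
|---|---|---|---|---|---|
| 3 | 4 | 48 | 304 | 151 | 71% |
| 3 | 8 | 122 | 306 | 208 | 49% |
| 3 | 12 | 166 | 305 | 235 | 28% |
| 3 | 24 | 224 | 303 | 265 | 0% |
| 0.5 | 4 | 134 | 435 | 300 | 22% |
| 0.5 | 8 | 215 | 383 | 314 | 0% |
| 0.5 | 12 | 244 | 357 | 312 | 0% |
| 0.5 | 24 | 273 | 329 | 308 | 0% |

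**Reading.** Every row has the same 45-minute level of 300 ng/ml. With fast absorption, that level overstates the interval average, and up to 71% of the interval lies below 200. With slow absorption, it is close to or slightly below the average, and it precedes the peak, which in this model comes about 3 h after the dose. In one slow-absorption row the peak passes 400. Against a floor of 300, the 12-hour level is too low in every row.

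**The case against.** The strongest reply is that the plan already exposes most of this. The pre-dose mean and SD at T6 and T7 will be reported beside the 45-minute values, so a shortfall would be visible to anyone who looked. That stands: the gap lies in what is compared with the target, and data collection is adequate.

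Second, a reader might infer that the trial will formally declare the target met, or that 1b decides how null craving or drinking results are read. The documents support neither. Section 21.3.2 only reports a mean and SD for 1b, and nothing makes 1b a gate for Hypotheses 2a, 2b or E.

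Third, a reader might infer that the pre-dose level has to be in range for exposure to count as adequate. The documents do not say whether peak, average or trough drives the effect, or when the rodent serum was sampled. Section 3.2.1 reports effects on alcohol seeking up to 138 days after treatment, so effects there outlasted exposure. The natural counterpart of continuous release is the interval average, which neither sample gives directly. Section 3.2.3 also bridges to oral dosing through a rat study that merely attained the range, although that study measured levels and is not the efficacy benchmark. This rules out a mandatory pre-dose criterion, but it equally gives no ground for relying on 45 minutes alone.

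Fourth, the kinetics are assumed, and the 45-minute sample may understate exposure. That also stands, and it is a reason to use both samples.

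**Conclusion.** The point holds in limited form. As written, 1b and the target-level check can support a claim of comparable exposure from one point on an intermittent profile, although a second point from the same visit is available and is never set against the target.

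The size cannot be fixed from the documents. From 300 ng/ml at 45 minutes, simple decline puts the 12-hour level anywhere from 43 to 217 ng/ml for half-lives of 4 to 24 h. Under slow absorption with a half-life of 8 h or more, no part of the interval falls below 200. These are illustrations under assumed kinetics, and the number of cases below 200 says nothing about likelihood. The schedule's peak label does not show that 45 minutes is the peak, so the single sample can err in either direction.

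The stronger reading, that exposure will in fact be inadequate for much of each day, is not supported. Separately, the two target ranges conflict, and the answer for a given level can depend on which is used.

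**What to change.** In Sections 21.3.2 and 21.3.4, or in the formal SAP that Section 21.1 says will be written before database lock and unblinding:

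1. At T6 and T7, compare both the 45-minute and the 12-hour pre-dose CBD levels with the target range.
2. For each level, report the mean, the SD and the proportion of CBD participants below, within and above the range.
3. Word the 1b conclusion by sampling time. If only the 45-minute level is in range, conclude that the range was reached 45 minutes after dosing, not that exposure was comparable across the interval.
4. Do not make the pre-dose level a mandatory pass/fail condition.
5. Reconcile the range between Sections 4.1 and 21.2 (200-400 ng/ml) and Section 3.2.3 (300-400 ng/ml), and state one range before unblinding.

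The cost is a few sentences and some extra table rows, with no new samples or assays. The downside is that the 1b statement may be less favourable.
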